2.5 Study flow chart

	Treatment (24 Months)											Post-treatment follow-up (4 weeks) ^{8,9}
Month	0 ¹	2	4	6	8	10	12	15	18	21	24	
Day (+/- 7 days)	0	61	122	183	243	304	365	456	547	638	730	
Visit Number ²	0	1	2	3	4	5	6	7	8	9	10	NA
Clinic Visit	X	X	X	X	X	X	X	X	X	X	X	
Incl/Excl criteria	X											
Vital signs	X	X	X	X	X	X	X	X	X	X	X	
Physical exam.	X	X	X	X	X	X	X	X	X	X	X	
Conc. Med.	X	X	X	X	X	X	X	X	X	X	X	X
eGFR ³	X	X	X	X	X	X	X	X	X	X	X	
Plasma Oxalate	X	X	X	X	X	X	X	X	X	X	X	
Stone events ⁴	X	X	X	X	X	X	X	X	X	X	X	X
Echocard. ⁵	X			X			X		X		X	
Ultrasound	X						X				X	
Safety Labs ⁶	X	X	X	X	X	X	X	X	X	X	X	
Stool	X			X			X		X		X	X
24-hour urine	X		X		X		X		X		X	
Quality of Life	X			X			X		X		X	
Pregnancy test ⁷	X										X	
Review Adverse events	X	X	X	X	X	X	X	X	X	X	X	X
Drug dispense/ Accountability	X	X	X	X	X	X	X	X	X	X	X	

¹ Month 0 (Visit 0; reference time point) will be the same as the last visit (Week 52) in ePHex. For echocardiography of the heart and ultrasound of the kidneys, week 48 measurements in ePHex are considered Month 0. If there is no seamless transition (delay >1 month) from ePHex, a new clinic visit 0 (Month 0) will take place with applicable measurements prior to first dose of open label Oxabact[®] and further assessments should follow according to schedule.

² Visit window during treatment period +/- 7 days. In the case of an acute kidney injury occurring close to a scheduled visit, the visit will be rescheduled to ensure that the AKI does not adversely affect values (especially for eGFR). The days on which each visit should occur are detailed in Table 6 of the protocol.

³ As determined by the Schwartz equation for children (age below 18), and CKD-EPI equation for adults (age 18 or above) based on serum creatinine.

⁴ Kidney stone events and related symptoms will be captured at every visit, including events in between visits.

⁵ Echocardiography to be done within +/- 2 weeks of the clinic visit at months 6, 12 and 18. If the images fail quality criteria, the examination will be repeated within 4 weeks.

⁶ Safety Labs will include blood and urine sampling.

⁷ If applicable.

⁸ A post-treatment safety follow-up will be performed as a telephone call (the safety follow-up period will cover a duration of four weeks and the telephone call will be made maximum 3 working days after the safety follow-up period).

⁹ Subjects will provide a post-treatment follow-up stool sample 4 weeks (plus maximum 3 working days) after intake of last dose of study drug.

3 PATIENTS FOR ANALYSIS

3.1 Analysis populations

3.1.1 Full-Analysis-Set (FAS)

The FAS includes all subjects who have received at least one dose of the investigational drug during the ePHex-OLE study and have at least one efficacy assessment during the ePHex-OLE study. This population will be used for the analysis of efficacy.

3.1.2 Safety-Analysis-Set (SAF)

The SAF includes all subjects who have received at least one dose of the investigational drug during the ePHex-OLE study. Safety summaries will be based on the SAF.

4 DATA REVIEW MEETING

Prior to database lock, data issues and protocol deviations and their impact on the statistical analyses will be discussed during the Data Review Meeting (DRM). For efficiency reasons, a pre-DRM may be held when data from a selection of subjects is cleaned, mainly to assess data quality. Invitees to these meetings are the OxThera Chief Medical Officer (CMO), the OxThera statistician, the OxThera and PSR/Ergomed Project Manager (PM), the PSR/Ergomed Lead Data Manager (DM) and the Author! /Certara Lead Statistician, but more roles can be invited if considered necessary. Input to the DRM will be supplied by PSR/Ergomed PM/Data Management at least one week in advance of the meeting: a list of all protocol deviations (including missing and outlier data), with specific detailing and description regarding the deviation. Other relevant data may also be shared by PSR/Ergomed for discussion. Furthermore, programmed data output as agreed will be shared by the Author!/Certara Lead Statistician.

The goal of this meeting is to reach consensus on data quality, meaning that we are confident that the database can be considered clean, no outstanding issues remain, and assess (important) protocol deviations to interpret a possible impact on the proposed statistical analyses.

The decisions taken during the meeting will be documented by the PM (or a delegate as agreed) and sent for review to all parties involved as soon as possible after the meeting, but before database lock. Once all parties involved agree with the documented decisions, the document is finalized and signed by all attendees before database lock, and stored by the PM.

Furthermore, the COVID-19 impact will be evaluated. Possible decisions regarding additional analyses may be applicable, following the COVID-19 addendum.

5 PROTOCOL DEVIATIONS

Protocol deviations will be identified to the extent possible by individuals responsible for data collection/compliance, and its analysis and interpretation. Prior to database lock, deviations will be classified as important or not important and any data values excluded from analysis will be identified, along with their reason for exclusion. This includes PDs classified for their relation to COVID-19.

6 STUDY ENDPOINTS

6.1 Primary endpoint

The primary endpoint is change from baseline in kidney function (eGFR) after 12 and 24 months of open-label Oxabact treatment.

6.2 Key secondary endpoint(s)

The secondary endpoints are the following:

- Change from baseline in total plasma oxalate concentration after 12 and 24 months of open-label Oxabact treatment.
- Frequency of kidney stone events after 12 and 24 months of open-label Oxabact treatment. Stone events are defined as:
 - Patient- or investigator reported symptoms, or
 - Stone passages or removals, or
 - Increase in number of stones assessed by ultrasound.

6.3 Other endpoint(s)

In addition, a set of other endpoints are specified, which are considered supportive to the primary and key secondary endpoints:

- Change from baseline in myocardial function as measured by Speckle Tracking and traditional echocardiography.
- Change from baseline in free plasma oxalate concentration.
- Change from baseline in urinary oxalate excretion.
- Grade of nephrocalcinosis as assessed by Ultrasound.
- Change in number of *O. formigenes* in stool.
- Association between change in number of *O. formigenes* in stool and change in total plasma oxalate concentration.
- Change from baseline in score of Quality of Life questionnaire.
- Change from baseline after 12 and 24 months of open-label treatment in markers for renal function, renal tubular capacity and inflammation
 - Urine: magnesium, phosphorus, citrate, calcium, glycolate, creatinine, urea, calcium oxalate crystals, pH, osmolality and urinary volume.
 - Blood: magnesium, phosphorus, citrate, calcium, BUN, ALP, bicarbonate, CRP, WBC, creatinine and Cystatin-C.

6.4 Safety endpoint(s)

The safety parameters to be evaluated are:

- Adverse events.
- Vital signs.
- Physical examination.
- Laboratory safety measurements: haematology, clinical chemistry and urinalysis.

7 STATISTICAL ANALYSIS

7.1 General considerations

Depending on the results from the ePHex study, three options for data analyses for ePHex-OLE are proposed:

- 1) If ePHex is positive, the SAP is followed completely as described, integration with ePHex data will be performed and all outputs will be based on CDISC data.
- 2) If ePHex is negative and the ePHex-OLE study is prematurely closed, the analysis for ePHex-OLE will be limited to simple listings and descriptive summaries for demographics, disposition, primary and key secondary efficacy, and exposure and safety, programmed on raw data following the FDA guideline on Abbreviated Reports¹. No statistical analysis will be performed, and no integration with ePHex (CDISC) data will be done, except for the use of randomisation information from ePHex.
- 3) If ePHex is ambiguous, an additional data evaluation will be done using an agreed selection of outputs, programmed on raw data and without integration with ePHex (CDISC) data, except for the use of randomisation information from ePHex. Following the results, option (1) or (2) will be further pursued.

For a number of analyses in this study, data from study ePHex will need to be integrated (see appendix referred in section 11.1). Efficacy analyses, summaries and graphical presentations will include pooled data from both the ePHex and ePHex-OLE studies based on the FAS, and will be presented both for the overall population and according to the randomisation ('as randomised') as applied in the ePHex study. Safety summaries will include the safety data reported in the ePHex-OLE study only and will be based on the SAF. Where applicable, presentations will be done per visit. Baseline data such as demographics, eligibility and prior medication has been collected for ePHex-OLE and will be presented without inclusion of ePHex data. Where presentations are done per treatment group, this will be as randomised during the ePHex study and these will be presented as (O - O) and (P - O), respectively, where O=Oxabact and P=Placebo. Historical data as collected during ePHex study will not be included and presented again. Lastly, change from baseline values will be calculated two different baselines: the baseline as per study ePHex, and as collected for study ePHex-OLE as supportive (only for the subjects that received placebo during ePHex).

Raw data (in listings) will be presented in the same precision as received. Appropriate rounding will be performed for the following summary statistics: arithmetic mean, LS mean, median, Q1 and Q3, SD (standard deviation), SE (standard error) and two-sided 95% confidence limits will be presented with at least one more decimal than the original data; minimum and maximum values will be presented with the same precision as the original data. In special cases, e.g. after conversion of data, the number of decimals will be determined based on relevance. In frequency tables, percentages will be presented with 1 decimal (except for 100%, if that is the maximum value), unless otherwise stated. P-values will be presented with 3 decimals, and those smaller than 0.001 will be replaced by <0.001.

Descriptive statistics presented in general summary tables will be the number of non-missing observations (n), arithmetic mean, SD, SE, median, Q1, Q3, minimum and maximum for quantitative data. For qualitative data, frequency counts and percentages will be determined. The

¹ <https://www.fda.gov/files/drugs/published/Submission-of-Abbreviated-Reports-and-Synopses-in-Support-of-Marketing-Applications.pdf>

denominator used when calculating percentages will be the number of subjects in the applicable analysis population. Statistical output will present LS means, SE and two-sided 95% confidence limits, where applicable. All plots will be created using scheduled protocol time or visit on the x-axis. Mean plots will be presenting mean +/- SE.

Baseline is generally defined as the last non-missing planned and valid measurement/assessment before first dose of study drug, unless otherwise specified. Unscheduled measurements are excluded as baseline value, unless otherwise specified. Change from baseline is calculated as the value at a specific time point minus the value at baseline. For this study, the following definitions are used to define the baseline measurement:

- The first baseline is defined as the baseline of the ePHex study, which is specified per ePHex SAP for each of the assessments.
- A second baseline is defined as the last planned measurement prior to open-label treatment in the ePHex-OLE study. This may be the last visit of the ePHex study or Visit 0 of the ePHex-OLE study, depending on whether the subject has a seamless transfer from one study to the other. If a Visit 0 result is available for a subject, it will be assumed the subject did not have a seamless transfer and that value will be used as the second baseline. This second baseline is only applicable for subjects that received Placebo treatment during ePHex.

For safety parameters, only the second baseline is used to calculate change from baseline. For efficacy parameters (eGFR, plasma oxalate, urine oxalate excretion, faeces, echocardiography, ultrasound, Quality of Life, renal markers), both baselines will be applied as applicable.

For all efficacy analyses, the observed values and the change from baseline will be presented in summary tables and plots.

A treatment emergent adverse event (TEAE) is defined as an adverse event reported on or after first dose date of study drug in the ePHex-OLE study and up to 4 weeks after last dose of open label medication in the study.

Collected data will be presented in individual data listings, and derived data will be added when needed. For all relevant listings, study day will be added. The calculation for this day is as described in the addendum as referred in section 11.1. All listings will include information on subject number, treatment ((O - O) and (P - O)), and age, race and sex information as collected during baseline of ePHex-OLE.

Considering the limited sample size, the statistical analyses proposed, beyond summaries and graphical presentations of the data collected, will only be performed as supportive and depending on the sample size. No formal statistical testing will be done and statistical significance will be viewed with caution, considering the very small and heterogeneous patient population. Any determined p-value can only be indicative. No correction for multiple comparisons will be applied for any of the endpoints.

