1 GENERAL

This Statistical Analysis Plan (SAP) describes in detail the methods and presentation of the data analyses which will be conducted by AUTHOR! et al. / Certara for study OC5-OL-02. This plan is written in agreement with protocol version 2, dated 06 July 2020, annotated CRF version 6.0, dated 28 August 2020, the relevant GCP-ICH guidelines and sponsor requirements. Additional changes or updates of those documents or requirements may result in a new version of the statistical analysis plan.

A signed version of the SAP for study OC5-OL-02 is preferably to be finalized before database lock and unblinding of study OC5-DB-02.

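### SAP 7.1 option 2 promises primary-efficacy summaries but excludes the ePHex baseline they need, and in the ambiguous case OLE outputs decide, without a criterion, how full the analysis is

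*SAP*

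**What the plan says.** SAP 7.1 opens its general considerations with a gate: "Depending on the results from the ePHex study, three options for data analyses for ePHex-OLE are proposed".

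- **Option 1:** "If ePHex is positive, the SAP is followed completely as described, integration with ePHex data will be performed".
- **Option 2** applies under two conditions: "If ePHex is negative and the ePHex-OLE study is prematurely closed". It keeps listings and descriptive summaries, including primary and key secondary efficacy, on raw data. It drops all statistical analysis, and "no integration with ePHex (CDISC) data will be done, except for the use of randomisation information from ePHex".
- **Option 3:** "If ePHex is ambiguous, an additional data evaluation will be done using an agreed selection of outputs". These outputs are also on raw data, with the same exclusion and the same exception for randomisation. Then: "Following the results, option (1) or (2) will be further pursued".

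On baselines, SAP 7.1 and 7.6.1 take the ePHex baseline as the primary one. Protocol 12.3 defines it for eGFR as the mean of three values taken before ePHex randomisation. SAP 7.1 restricts the second baseline to subjects who had placebo in ePHex, and says of its source: "This may be the last visit of the ePHex study or Visit 0 of the ePHex-OLE study".

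Protocol 12.3 has efficacy outputs draw on both studies and attaches no condition. The paragraph of SAP 7.1 that follows the three options says the same. SAP section 8, on changes from protocol, does not mention the three-option scheme. On timing, SAP section 1 says that the signed SAP is "preferably to be finalized before database lock and unblinding of study OC5-DB-02".

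**The concern.** Two things look wrong.

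First, option 2 commits to reporting an endpoint while shutting out the data that define it. A programmer following the text would have on-treatment eGFR and plasma oxalate, the randomised arm, and no value to subtract.

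Second, in the ambiguous case the sponsor sees selected OLE outputs, with the arms known, before deciding whether the full analysis is done. The two destinations differ greatly. Option 1 gives model-based estimates, confidence intervals and p-values at 12 and 24 months, with multiple imputation and ANCOVA alongside. Option 2 gives none of these. If that choice follows the results and has no stated rule, a reader of the final report cannot tell whether the depth of reporting was influenced by what was found.

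**Working it through.** No figure in the plan bears on this point, so the check sets the passages side by side.

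**Step 1. What each option admits.**

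| Option | Trigger | ePHex data admitted | Primary efficacy promised | Terminal? |
|---|---|---|---|---|
| 1 | ePHex positive | full integration | yes, full SAP | yes |
| 2 | ePHex negative and OLE closed early | randomisation information only | yes, descriptive | yes |
| 3 | ePHex ambiguous | randomisation information only | agreed selection, content not stated | no, passes to 1 or 2 |

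Counts: 3 of 3 options use some ePHex data, 2 of 3 exclude integration beyond randomisation, and 1 of 3 (option 2) is an end point without integration. In 1 of 3 (option 3), results choose the next step.

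**Step 2. What the primary endpoint needs.** Change = OLE visit value minus ePHex baseline. The second term lies in the ePHex data for every subject. Under option 2 read literally it is unavailable, so the change cannot be formed for eGFR. The same holds for total plasma oxalate, which SAP 7.6.2 analyses in the same way.

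**Step 3. Whether the second baseline can stand in.**
- O-O: not defined (SAP 7.1).
- P-O, seamless transfer: the last ePHex visit (week 52), so again an ePHex value.
- P-O, delay of more than 1 month: OLE Visit 0, which is available.

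Only the third group would have any change score, and it would not be the primary one. SAP 2.4 reports 18 subjects included but does not give the split by transfer type, so no count can be attached.

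**Step 4. Stone events.** Events recorded as AEs are counted from first to last OLE dose (SAP 7.6.2) and need no ePHex value. The ultrasound component is an increase in stone number. For seamless transfers its Month 0 reference is the ePHex week-48 scan (SAP 2.5, footnote 1), which option 2 also shuts out.

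**Step 5. Whether the options cover all cases.** Cross three ePHex outcomes with two OLE states:

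| | OLE continues | OLE closed early |
|---|---|---|
| Positive | option 1 | option 1 |
| Ambiguous | option 3 | option 3 |
| Negative | none | option 2 |

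One of 3 × 2 = 6 cells is empty.

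**Step 6. What decides in option 3.** The additional outputs carry no ePHex data except the arm, so the deciding results can only be OLE results, and they can be split by arm. The SAP gives no criterion for the three ePHex outcomes, for the selection of outputs or for the final choice. Option 3 can also lead to option 2 when neither of option 2's own conditions is met, for example with an ambiguous ePHex and an OLE that ran to 24 months.

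**The case against.** The strongest reply is about wording. The exclusion speaks of integration with CDISC data and is paired with programming on raw data, so it may limit only how datasets are built. On that reading raw ePHex baselines could still be merged, as the promise of primary efficacy implies, and the details may be in Addendum 1, which is not among the documents. This is a possible intention. However, the clause names a single exception, randomisation information, and nothing in the SAP permits or describes a merge of baselines. At best, the source of option 2's baseline is unstated.

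Second, the branches are disclosed in advance, and option 2 keeps descriptive summaries, which are the primary analysis anyway. What it drops is supportive and already conditional on sample size. That stands, and it limits the stakes. Early closure would also remove much of the 24-month data, though not where option 2 is reached through option 3.

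Third, a positive result may be defined in the ePHex SAP, which is not available here. That could settle the first gate but not the second step of option 3. Nor do the documents show late signing; branches that await an ePHex result suggest drafting before it was known.

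A reader might infer more than the text supports:
- That OLE results generally decide the analysis. The first gate is the ePHex result; OLE results decide only in the ambiguous case.
- That options 2 and 3 use no ePHex data. Both use the randomisation information.
- That two of three options lose the primary endpoint. Option 3 is intermediate, and if it leads to option 1 the endpoint is computed.
- That all key secondary efficacy is lost. AE-based stone events are unaffected.
- That type I error is inflated. SAP 7.1 plans no formal testing.

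**Conclusion.** The concern holds in a limited form. Followed literally, option 2 cannot produce the change from ePHex baseline in eGFR and total plasma oxalate that it promises to summarise, and the second baseline does not fill the gap. This contradicts Protocol 12.3 and the SAP's own next paragraph, and section 8 does not declare it. Separately, in the ambiguous case only, OLE outputs by ePHex arm choose between the full analysis and one with no statistical analysis, without a criterion. One of six combinations of ePHex outcome and OLE state has no branch.

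The size is one terminal option of three for the missing baseline, and one of three for the results-dependent choice. No subject count can be given for those left with no change score on either baseline, because the number of seamless transfers is not stated. The consequence is a risk of selective reporting in a descriptive study. The conclusion rests on taking the data exclusion at its word and on Addendum 1 and the ePHex SAP not overriding it.

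**What to change.** Amend SAP 7.1, section 1 and section 8 as follows.

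1. In every option, merge for the enrolled subjects the ePHex baseline and last-visit (week 52) eGFR and total plasma oxalate, plus the week-48 ultrasound reference. Report change from ePHex baseline.
2. Let the choice of option depend only on the ePHex result, as defined in the ePHex SAP and cited here, and on whether the OLE is closed early. Remove the step in which OLE results choose.
3. Send both the ambiguous case and the case of a negative ePHex with the OLE continuing to option 1. SAP 7.6.1 already falls back to descriptive output if the models cannot be run.
4. Delete the word preferably in section 1, so that the SAP is signed before ePHex unblinding.
5. List in section 8 whatever departure from Protocol 12.3 remains.

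The cost is SAP wording, a small data merge for the 18 included subjects, and some extra supportive analysis if ePHex is ambiguous or negative. An abbreviated report after a negative ePHex and early closure remains available; it would now carry its primary endpoint.

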7.2 Missing data

For handling missing data of the statistical analyses applied to the primary and key secondary endpoints, refer to the respective analysis sections. Other data will not be imputed unless specified. When dates are imputed, a flag will be provided to the CDISC datasets to show this is

an imputed rather than an actual date. Listings will only present the actual date, but any calculations can be done on imputed dates. Date imputations are listed below.

AE and prior/concomitant medication

Missing/incomplete information related to AEs and concomitant medications will be handled as listed below, when applicable. Following these steps using temporary programming will ensure that missing dates imputations uses the most conservative approach.

- In case of a missing stop date, the stop date will be imputed as follows:
 - In case stop date is partially missing:
 - If the day part is missing, and the month and year present then day will be set to the last day of the month.
 - If both day part and month part are missing, then day and month will be set to 31 December of that year.
 - If any of the above imputations would lead to a date after end of study, then the date of end of study will be used.
 - In case the stop date is completely missing and ongoing is not marked:
 - The event will be assumed to be 'ongoing'.
- In case of a partially missing onset/start date, and stop date is determined to be after first dose date (possibly after imputation), the start date will be imputed as follows:
 - In case start date is partially missing:
 - If the day part is missing, and the month is equal to the month of first dosing date, then day will be set to the date of first dose.
 - If the day part is missing, and the month is not equal to the month of first dosing date, then day will be set to the first day of the available month.
 - If both day part and month part are missing, then day and month will be set to January 1st of the year, unless if year is the same as first dose date year: then the date will be imputed with the first dose date.
 - In case the start date is completely missing:
 - If the stop date is earlier than the first dose date, then the start date will be set to Jan 1st of the stop year. If the stop date is on or after first dose date, then the start date will be set to first dose date.
- If stop date is before first dose date, then start date does not need an imputation, and the event or medication is considered to be prior.
- In case full start date and full stop date are missing, the start date will be imputed to first dose date.
- Missing severity will be imputed as severe (CTCAE grade 3).
- In case causality is missing for a certain TEAE, this will be regarded as related.
- In case seriousness is missing for a certain TEAE, it will be queried by DM. If the query is not resolved, an imputation of serious will be done, leading to a mismatch with the PV documentation.

In case other date imputations are performed (e.g. for the purpose of calculation of durations) a simple approach will be used:

- if the day is missing, the first of the month will be used
- if the month is missing, the first month of the year will be used
- if year is missing no imputation will be performed and the resulting calculation based on the date will be missing

